#### Visit 4 (Day 6-8)

Subject will return approximately 24 hours ( $\pm$  4 hours) after the first blood transfusion visit to MUH-CTRC.

- Blood draw approximately 24 hours following the first transfusion visit to test survival of BioRBCs
- Blood draw for clinical lab testing (CBC)
- AE assessment

Total blood volume drawn will be about 1 tablespoon (approximately 8 mls).

#### Visit 5 (Day 32-41)

This visit will be scheduled approximately a little over one month (ranges between 32-41 days) after completion of 1st transfusion in MUH-CTRC.

- Blood draw to test antibodies to BioRBCs. If anti-BioRBC antibodies are detected following 1st transfusion, the subject will be withdrawn from the study. A negative test result must be confirmed prior to proceeding with 2nd transfusion.
- Blood draw for Type and Cross (ABO/Rh type and antibody screen) prior to transfusion
- AE assessment

Total blood volume drawn will be about 1 tablespoon (approximately 10 mls).

Visit 6 (Day 35-42) This visit will be scheduled between approximately 35-42 days following blood donation in MUH-CTRC. A “Physician’s Processing Request form” will be sent to the HSCLab staff via the UPMC secure email system. This form will have the subject’s private health information and the study ID number that is reviewed and signed/dated by the PI or Co-I in this study. In order for the blood to be released from HSCLab to CTRC, HSCLab will need this form. The Vitalant form, “Patient Identification Form” that is sent to HSCLab by the study team via the UPMC secure email system will contain the subject’s private health information and study ID

number. In order for the blood to be released from Vitalant to HSCLab on the day of biotinylation, Vitalant will need this form.

- Brief physical examination to include vital signs (Temp, HR, RR, BP, pulse ox)
- Review medical history and demographics
- Urine pregnancy test in women of childbearing potential
- Blood draw for whole blood sample will be sent to Wake Forest University
- Blood draw for clinical lab testing (CBC)
- Blood draw prior to transfusion to detect presence of BioRBCs. Results not needed to proceed with the study.
- Transfuse 150 mL of 35-42 days old biotin-labeled RBCs
- Obtain the subject's leftover BioRBCs in IV line/unit of blood for storage and stress hemolysis
- Vital signs (Temp, HR, RR, BP, pulse ox) approximately every 15 minutes during the transfusion and approximately 15 minutes post transfusion
- Blood draw approximately 2-4 hours post transfusion to determine baseline for 35-42 days old BioRBCs.
- AE assessment
- Given meal

Total blood volume drawn will be about 2 tablespoons (approximately 14 mls).

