Final biotin concentrations after transfusion (recipient circulation) are 0.2 µg/mL and 0.04 µg/mL, days 5-7 and 35-42, respectively. Subjects will be closely monitored for evidence of transfusion reactions, and vital signs will be taken at baseline and every 15 minutes during the transfusion and then 15 minutes after the transfusion ends by qualified personnel at the Clinical Translational Research Center (CTRC) of UPMC Montefiore Hospital (MUH-CTRC).

To evaluate RBC post transfusion survival, blood samples will be taken to quantify biotin labeled RBCs pre-transfusion and at 2-4 hours, 1 month and 2 months after each transfusion. Additional blood samples will be obtained at Visit 1 for naturally occurring to anti-BioRBC antibodies and on Day 35-42 and Day 125-150 to evaluate the formation of antibodies to the biotinylated RBCs and any signs of hemolysis. The overall study design is depicted in Figure 1 below.

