### Visit 3 (Day 5-7)

This visit will be scheduled between approximately 5-7 days following blood donation in MUH-CTRC. A "Physician's Processing Request form" will be sent to the HSCLab staff via the UPMC secure email system. This form will have the subject's private health information and the study ID number that is reviewed and signed/dated by the PI or Co-I in this study. In order for the blood to be released from HSCLab to CTRC, HSCLab will need this form. The Vitalant form, "Patient

Identification Form” that is sent to HSCLab by the study team via the UPMC secure email system will contain the subject’s private health information and study ID number. In order for the blood to be released from Vitalant to HSCLab on the day of biotinylation, Vitalant will need this form.

- Brief physical examination to include vital signs (Temp, HR, RR, BP, pulse ox)
- Urine pregnancy test in women of childbearing potential
- Blood draw for whole blood sample will be sent to Wake Forest University
- Blood draw for clinical lab testing (CBC)
- Blood draw prior to transfusion to detect presence of BioRBCs. Results not needed to proceed with the study.
- Transfuse 150 mL of 5-7 days old BioRBCs
- Obtain the subject’s leftover BioRBCs in IV line/unit of blood for storage and stress hemolysis
- Vital signs (Temp, HR, RR, BP, pulse ox) approximately every 15 minutes during the transfusion and approximately 15 minutes post transfusion
- Blood draw approximately 2-4 hours post transfusion to determine baseline survival for 5-7 days old BioRBCs.
- AE assessment
- Given meal

Total blood volume drawn will be about 2 tablespoons (approximately 14 mls).

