#### **6.4.8. Withdrawal of Subjects and Stopping Criteria:**

##### **STOPPING RULES:**

**Withdrawal of Subjects:** Subjects must be withdrawn from the study for the following reasons:

- An SAE or a serious post-infusion hemolytic event that is determined to be possibly, probably, or definitely related to the infusion of autologous BioRBC.
- Detection of anti-BioRBC antibodies following first infusion. In the unlikely event that a study subject tests positive for bioRBCs following first infusion, the subject will be withdrawn from

the study. The subject will not receive the subsequent RBC infusion. Since anti-BioRBC antibodies attack BioRBCs, the 2-4 hours post transfusion survival and mean lifespan measurements will be affected. Based on the time of discovery, the 2-4 hours time point measurement may be retained or discarded. The participant will be followed for signs and symptoms of hemolysis as well as the disappearance of the anti-biotinylated RBC antibodies.

Subjects may be withdrawn from the study for the following reasons:

- In the unlikely event that a stored unit does not pass the endotoxemia test, red blood cells will not be transfused and will have to be withdrawn from the study.
- In the event that a donated RBC unit is misplaced, the subject's participation in the study will be terminated since an autologous transfusion will no longer be possible.
- At their own request
- At the specific request of the Investigator (eg detection of a new significant safety concern related to the study drug).
- Occurrence of intercurrent diseases which in investigator's opinion, continuation of the study drug would be harmful to the subject's well-being.
- Pertinent non-compliance with the conditions for the trial or instructions by the investigator.
- Lost to follow up

Any subject removed from the study will remain under medical supervision until the condition is medically acceptable. Study subjects removed from the study will be replaced by enrolling another volunteer with similar demographic

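### The Visit 5 scheduling sentence puts the antibody check at day 37-48 from donation, so the result that must clear the second transfusion can come after that transfusion's day 35-42 window

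*Combined protocol and SAP*

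**What the plan says.** The timing of the antibody check before the second transfusion appears in five places.

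- **Visit 5 heading, section 2.2.2:** "Visit 5 (Day 32-41"), with no anchor named.
- **Visit 5 scheduling sentence, same section:** "scheduled approximately a little over one month (ranges between 32-41 days) after completion of 1", the sentence going on to name the first transfusion.
- **Section 2.3.4:** plasma for anti-BioRBC antibodies on Day 32-41.
- **Appendix A:** Visit 5 at Day 32-41, with the antibody test marked there.
- **Section 2.2.1:** samples "on Day 35-42 and Day 125-150 to evaluate the formation of antibodies to the biotinylated RBCs".

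The two transfusions are tied explicitly to donation. For Visit 3: "This visit will be scheduled between approximately 5-7 days following blood donation in MUH-CTRC". For Visit 6: "This visit will be scheduled between approximately 35-42 days following blood donation". Section 2.3.2 repeats both windows.

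Visit 5 is a gate. Its text says "A negative test result must be confirmed prior to proceeding with 2" (the second transfusion). For a subject with antibodies after the first infusion, section 6.4.8 says "The subject will not receive the subsequent RBC infusion". The Visit 5 list also includes the Type and Cross before transfusion, and Appendix A marks type and screen only at Visits 1 and 5.

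**The concern.** The same range, 32-41 days, is used twice with what appear to be different starting points. The heading has to be read on the donation scale to fit the labels of Visits 3 and 6. The sentence beneath it starts the count at the first transfusion, about a week later. A coordinator booking from the sentence would often schedule the antibody draw too late to clear the infusion it is meant to clear.

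There is little room for slippage. Section 1.3 gives a 42-day shelf life for stored red cells, and section 2.4 defines the primary endpoint on cells stored 35-42 days. If staff wait for the result, as the protocol requires, the stored-blood infusion is either not given or given outside its window. A subject without that infusion contributes nothing to the primary comparison, in which section 2.5.1 plans groups of 15 against 20. The Type and Cross drawn at Visit 5 would be late for the same reason.

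**Working it through.** **Inputs**

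- First transfusion: T1 = 5, 6 or 7 days after donation (Visit 3; section 2.3.2).
- Visit 5 offset in the scheduling sentence: d = 32 to 41 days after T1.
- Second transfusion: 35 to 42 days after donation (Visit 6; section 2.3.2).

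**Step 1. Can the heading's Day 32-41 be reproduced from the sentence?**

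Visit 5 day from donation = T1 + d.

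- Earliest: 5 + 32 = 37.
- Latest: 7 + 41 = 48.

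The sentence gives day 37-48, so it does not reproduce Day 32-41. In the other direction, Day 32-41 counted from donation is 32 - 7 = 25 to 41 - 5 = 36 days after the first transfusion, which is not 32-41. The two statements cannot describe the same window.

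**Step 2. Compare the sentence with the Visit 6 window.**

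There are 3 first-transfusion days and 10 offsets, so 30 whole-day combinations.

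| T1 | Visit 5 range | By day 41 | On day 42 | After day 42 |
|---|---|---|---|---|
| 5 | 37-46 | 5 | 1 | 4 |
| 6 | 38-47 | 4 | 1 | 5 |
| 7 | 39-48 | 3 | 1 | 6 |
| Total | 37-48 | 12 | 3 | 15 |

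- After day 42: 15 of 30.
- On or after day 42: 3 + 15 = 18 of 30. This applies if a sample drawn on day 42 cannot be reported before an infusion that day.
- The earliest Visit 5 is day 37, so a second transfusion on day 35 or 36 could never be preceded by the test.

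**Step 3. Check by interval.**

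The two transfusions are 35 - 7 = 28 to 42 - 5 = 37 days apart. Offsets of 38 to 41 days therefore miss the window whichever first-transfusion day applies.

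**Step 4. Does the counting convention matter?**

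Donation is Visit 2, labelled Day 1. If the labels count donation as Day 1, the first transfusion is 4-6 days after donation and Visit 5 is 4 + 32 = 36 to 6 + 41 = 47 days after it, against a Visit 6 window of 34-41. Everything shifts by one day and the conflict is unchanged.

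**Step 5. Section 2.2.1.**

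Its Day 35-42 matches neither the heading nor the sentence. It is the label of Visit 6, yet neither the Visit 6 procedure list nor the Visit 6 column of Appendix A includes an antibody test.

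**The case against.** The strongest reply is that this is one mis-anchored phrase. The heading, section 2.3.4 and Appendix A agree on Day 32-41. Read from donation, that window opens before Visit 6 opens and closes before day 42, so the gate can be met. That is a fair account of how the text may have arisen, and it limits the fault to a few lines. It does not remove the fault: the sentence is the operative scheduling instruction and states its own anchor and range, while the heading states no anchor. The word approximately does not absorb an overrun of up to 48 - 42 = 6 days against a window that ends at the stated shelf life.

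A reader might infer that subjects will be transfused without antibody clearance. The documents do not support that. The Visit 5 text requires a confirmed negative result first, section 6.4.8 bars a further infusion after a positive one, and Visit 5 is numbered and tabulated before Visit 6. Proceeding without the result would breach the protocol. Section 2.3.3 also reports that in an earlier study antibodies appeared 4-5 months after infusion, were transient, and did not affect recovery or survival. None of this excuses an unclear gate, but the plan should not be described as exposing subjects to ungated transfusion.

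A reader might also treat the overlap of Day 32-41 with Day 35-42 as a second error and count day pairs in the wrong order. That would treat the two visits as scheduled independently, whereas the gate makes Visit 6 conditional on Visit 5. Overlapping windows are acceptable when the order is stated, as it is here.

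Finally, section 2.2.1 is an overview and does not identify its sample as the gating test. Its Day 35-42 is a mismatch to correct, not separate evidence that the gate fails.

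**Conclusion.** The point holds as an internal inconsistency in the visit schedule that should be corrected. Read as written, the Visit 5 sentence gives day 37-48 from donation, against Day 32-41 in three other places and Day 35-42 in a fourth. Half of the permitted combinations (15 of 30) fall after the second-transfusion window has closed. To say that most do (18 of 30) requires the further assumption that a day-42 sample cannot be cleared that day. Section 2.3.4 lists a 30-minute incubation and a 10-minute spin but gives no reporting time, so same-day clearance is neither established nor excluded.

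The counts weight whole days equally. They show what the text permits and do not forecast how visits are booked; nothing in the documents shows that staff have scheduled this way. The donation anchor for the heading is inferred from Visits 3 and 6. With the gate in force, the expected harm is a missed or out-of-window stored-blood infusion, with loss of that subject's primary-endpoint data, and a late Type and Cross. Section 6.4.8 provides for replacing subjects who are removed, but a missed storage window is not among its listed reasons, so it is unclear that replacement would apply.

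**What to change.** Reconcile the Visit 5 scheduling sentence, the Visit 5 heading, section 2.2.1, section 2.3.4 and Appendix A to one named anchor and one window. The window should allow the Visit 5 antibody result and the Type and Cross to be available before Visit 6 within the stated storage period. Stating how long the antibody result takes would settle whether a same-day draw can serve. Which days to use is for the sponsor to decide.

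The cost is a wording amendment to the visit schedule, submitted for IRB approval as section 4 requires. It need not add a visit, a sample or a subject, and the analysis is unchanged.

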#### Visit 7 (Day 36-43)

Subject will return approximately 24 hours ( $\pm$  4 hours) after the second blood transfusion visit to MUH-CTRC.

- Blood draw approximately 24 hours following the second transfusion visit to test survival of BioRBCs
- Blood draw for clinical lab testing (CBC)
- AE assessment

Total blood volume drawn will be about 1 tablespoon (approximately 8 mls).

#### Visit 8 (Day 65-72)

This visit will be scheduled between approximately 65-72 days, approximately 2 months post 1st transfusion or 1 month post 2nd transfusion in MUH-CTRC.

- Vital signs (Temp, HR, RR, BP, pulse ox)
- Blood draw to determine BioRBC survival.
- Blood draw to test antibodies to BioRBCs.
- Blood draw for clinical lab testing (CBC)
- AE assessment

Total blood volume drawn will be about 1 tablespoon (approximately 12 mls).

#### Visit 9 (Day 95-102)

This visit will be scheduled between approximately 95-102 days, approximately 2 months post 2nd transfusion in MUH-CTRC.

- Vital signs (Temp, HR, RR, BP, pulse ox)
- Blood draw to determine BioRBC survival.
- Blood draw for clinical lab testing (CBC)

- AE assessment

Total blood volume drawn will be about 1 tablespoon (approximately 12mls).

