### **2.2 DETAILED DESCRIPTION OF STUDY DESIGN**

## 2.2.1. STUDY DESIGN OVERVIEW

[figure not shown]
Subjects for autologous blood reinfusion studies will be selected in 2 ways. First healthy individuals without any known candidate SNPs will be identified as controls. A subset of REDSIII RBC Omics donors with candidate SNPs will be recalled to provide a blood sample to be tested for functional effects on red cell biophysical properties, stability in storage, and release of eDAMPs, compared to donors with no implicated SNPs. (See 2.2.3) We will develop an enriched SNP profile that defines a high risk and low risk donor for further evaluation in autologous reinfusion studies as a low cost precision transfusion medicine array.

Autologous reinfusions studies: Potential subjects will undergo a screening visit to determine that eligibility requirements are met. Subjects who meet the inclusion criteria and none of the exclusion criteria will be scheduled within 4 weeks of screening for a baseline assessment.

Eligible subjects will donate a unit (500 mL) of whole blood at one of the Central Blood Bank (Vitalant Pittsburgh) locations licensed by FDA. The blood will be processed and leukoreduced into a packed RBC unit (300-350 mL) according to standard procedures. This unit will then be split into two bags, with equal volume, labeled as “Autologous” RBC unit and stored under standard blood bank conditions in the blood bank under the supervision of [name]. Units will be preserved in adenine, dextrose, sorbitol, sodium chloride and mannitol (ADSOL) solution and stored in a monitored temperature controlled refrigerator at 1-6° until needed, according to standard blood-banking practice. That is, half of a unit (150 mL) will be stored for 5-7 days, and the second half will be stored for 35-42 days. Stored RBCs will be labeled with biotin (i.e. biotinylated autologous red blood cells) at 15 µg/mL on the day of infusion and administered intravenously on 5-7 days, and the second half will be labeled at 3 µg/mL on the day of infusion and administered intravenously into the same subject on 35-42 days.

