maximum of 6 times within one year. If the RBC-OMICs control subject does not want to perform an additional optional blood draw visit, the biotin study team will ask the other RBC-OMICs control subjects to participate in the additional optional blood draw visit. If an RBC-OMICs control subject will have an additional optional blood draw visit scheduled on the same day as an RBC-OMICs biotin subject with one of the targeted SNPs, the biotin study team will coordinate both subjects schedules to have them come into MUH-CTRC another day for the same day blood draw visit. Each RBC-OMICs control subject will not exceed the blood donation volumes (approximately 500 mls) within a 8 week period with the timing of each additional optional blood draw visit and/or any unrelated blood donations. The biotin study team will verbally ask the RBC-OMICs control subjects if they donated whole blood or red blood cells within 56 days prior to scheduling each blood draw visit. An RBC-OMICs control subject will not come more often than once a week for an additional optional blood draw visit at MUH-CTRC. The RBC-OMICs subjects will not be asked to donate with the same week per expedited review guideline for blood draw. The biotin study team under the direction of the PI will monitor each RBC-OMICs control subject's blood draw visits and each RBC-OMICs control subject's total number of blood draws to be in compliance with the protocol; not to exceed 6 times in one year. If the RBC-OMICs biotin subject with one of the targeted SNPs has abnormal red blood cell biophysiological properties, then the length of time from the subject's blood draw visit to when and if the subject can enroll in the biotin study (if qualifying) could vary by several months.

- Obtain written consent.
- Blood draw samples for [name] lab to test for in vitro studies of RBC membrane structure and function, RBC cellular response to oxidative stress, response to mechanical and storage stress, and RBC cellular metabolism. Other in vitro tests may be developed and performed.
- Blood draw sample for Wake Forest University to test for RBC hydration and water/ion transport.
- Blood draw sample to Vitalant to test for ektacytometry and RBC aggregation assays. [name] lab to help facilitate the processing of samples for [name] lab, Wake Forest University, and Vitalant.
- Samples may be sent to Yale University for other vitro tests.
- AE assessment

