### **2.3.7 Concomitant Medications**

Subjects will be advised to avoid any nutritional supplement containing biotin (Vitamin B7) and to refrain from eating raw eggs 30 days prior to blood donation and throughout the study period. Potential subjects will be requested to bring a list of any over the counter drugs and/or any nutritional or herbal supplements that they may be taking to the initial screening visit. This list will be documented in the research chart and carefully evaluated by the Physician Investigator for potential interactions with biotin. The Physician Investigator will have final decision regarding the acceptability of concomitant medications. Subjects will be requested to contact the research team prior to taking any new medications (including over-the-counter drugs and vitamin or herbal supplement) during their participation in the clinical investigation.

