## **2.4 STUDY ENDPOINTS**

### Primary Endpoint:

The primary endpoint is the labeled red blood cell recovery rate over 60-days post transfusion (using data from 2-4 hours, 1 and 2 month) of 35-42 day stored Bio-RBCs from blood donors with specified genetic mutations, compared with control subjects without the specified mutation.

This protocol may evaluate up to eight (8) genetic mutations as independent studies, compared with pooled control groups, as well as a group of subjects on testosterone replacement therapy. The eight genetic mutations that we will evaluate may include sickle cell trait (AS), and single nucleotide polymorphisms (SNPs) in ankyrin 1 (ANK1), glucose-6-phosphate dehydrogenase X-linked (G6PD), piezo-type mechanosensitive ion channel component 1 (PIEZ01), spectrin alpha

(SPTA), extended synaptotagmin-like protein 2 (ESYT2), Myo9b, and SEC14. We may identify additional SNPs as our analysis of the REDS-III GWAS study advances that could replace one of these SNP groups and/or we identify additional non-synonymous SNPs that are associated with susceptibility to hemolysis of stored red blood cells. In addition we will evaluate 15 subjects on testosterone replacement therapy with 20 controls that are gender and race matched that are not on testosterone replacement therapy. Each group will be considered a separate study for statistical purposes. Controls will be selected based on not having any of the SNPs that will be evaluated in these studies.

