### 2.5.2 Statistical Analysis

The primary assessment of RBC transfusion efficacy is post transfusion survival. Data from RBC recovery at 2-4 hours, 1 month and 2 months after each transfusion will be evaluated using mixed effect model (with restricted maximum likelihood variance estimator and bootstrapping) to calculate the effect of time, genetic group and their interaction on RBC survival. RBC recovery at each time point will be performed using the equation below.

$$\text{Percent survival (\%)} = \frac{\text{BioRBCs in circulation at } T_y \text{ (} 1 \leq y \leq 120 \text{ days)}}{\text{Baseline BioRBCs in circulation at } T_0 \text{ (20 min following RBC infusion)}} * 100$$

Secondary endpoints: The equation above will be used to define the 2-4hours post transfusion survival of BioRBCs. The other endpoints test for changes in RBC predisposition to hemolysis in cold storage by quantifying the rates of storage, osmotic, mechanical and oxidative hemolysis and the formation of RBC membrane-derived microvesicles. A sample size of 8 samples would detect a 10% difference in our assays' outputs with a power of 85%. We will use commercial software for statistical analyses (STATA version 15.0, StataCorp., College Station, Texas, USA). We will use mixed effect model (with restricted maximum likelihood variance estimator and bootstrapping) to calculate the effect of time, genetic group and their interaction on RBC survival. Normality tests will help to determine the appropriate transformation of outcome data. We will also use nonlinear term of time in these models (if applicable). We will use marginal test (from the primary models) to assess the effect of genetic group on 60-days and 2-4hours RBC survival separately. As a confirmatory analysis, Wilcoxon signed rank test will determine the differences between two groups for 60-days and 2-4 hours survival rate as well. The hypotheses will be tested primarily in old blood. A separate analysis will be performed in fresh blood transfusion as well. All P value <0.05 will be reported as statistically significant.

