### **3.3 EXCLUSION CRITERIA**

Subjects meeting any of the following exclusion criteria at baseline will be excluded from participating in study:

- Subjects with a past medical history or symptoms of blood dyscrasia, diabetes mellitus, hyperlipidemia, obstructive sleep apnea, renal disease, congestive heart failure, significant cardiac disease and / or known peripheral arterial disease.
- Moderate to severe systemic hypertension, (systolic blood pressure >140 mmHg and/or diastolic blood pressure > 95 mmHg)
- Systolic blood pressure <100 mmHg and/or diastolic blood pressure < 60 mmHg on the study day.
- Positive Direct Antiglobulin Test (DAT)
- Consumption of biotin supplements or raw eggs within 30 days
- Treatment with antibiotics in the week before initiating study participation to avoid suppression of erythropoiesis, which may accompany infection.
- Blood loss in the previous 8 weeks due to epistaxis, trauma, hemoptysis, gastrointestinal bleeding, diagnostic phlebotomy (> 30ml)
- Subjects who report tobacco or marijuana smoking within 6 months of study.
- Cognitively impaired subjects, or institutionalized persons and subjects unable or unwilling to complete written informed consent
- Subjects with a history of blood donation within the last 56 days.
- Use of other investigational drugs/devices within 30 days of screening.
- Subjects taking any medication for the treatment of diabetes including insulin
- Females of childbearing potential who are pregnant or unwilling to undergo pregnancy testing; females with positive pregnancy testing on screening day will be excluded.
- History of prior transfusion reaction to blood products.
- Allergic reaction to biotin
- Donors with naturally occurring antibodies against BioRBCs will be excluded from the study

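### After baseline the protocol neither discourages nor records blood donation by infusion subjects, so a donation during the 60-day follow-up would be read as lost red-cell survival

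*Combined protocol and SAP*

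**What the plan says.** The baseline exclusions in Section 3.3 include "Subjects with a history of blood donation within the last 56 days". They also cover recent blood loss, with a 30 mL figure attached to diagnostic phlebotomy.

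The advice in Section 2.3.7 that runs through the study covers biotin supplements, raw eggs and new medicines. It does not cover giving blood.

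Section 2.2.2 and Appendix A schedule the survival draws. Visits 8, 9 and 10 each list "Blood draw to determine BioRBC survival", vital signs, a CBC and an adverse event assessment; Visit 8 and Visit 10 add antibody testing. The last medical history review is at Visit 6, the day of the second transfusion.

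One group is asked about donation during the study, namely the controls who give blood only for in vitro testing: "The biotin study team will verbally ask the RBC-OMICs control subjects if they donated whole blood or red blood cells within 56 days", before each draw is scheduled (Section 2.2.2, Blood draw visit).

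The primary endpoint (Section 2.4) is recovery of the 35-42 day stored cells over 60 days, from samples at 2-4 hours, 1 month and 2 months. On its calculation, Section 2.5.2 says "RBC recovery at each time point will be performed using the equation below"; the equation divides labelled cells in circulation at the later time by labelled cells at baseline. Neither it nor Section 2.5.3 on missing data mentions blood that has left the body.

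**The concern.** A donation takes labelled cells out of the circulation without any of them dying. The survival ratio cannot separate the two, so a subject who donates appears to have poorer red-cell survival. If donation is more common in one group, the comparison is biased. If it is equally common, recovery is understated in both groups and noise is added to groups of 15 and 20, and to the correlations with in vitro hemolysis planned in Section 2.4.

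The plan treats donation as important enough to exclude on at entry and to ask about in the in vitro controls. The infusion subjects, on whom the primary endpoint is measured, are not asked. A donation that is not recorded at the time cannot be reliably reconstructed later.

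**Working it through.** **Timing.** The study donation is on Day 1 (Visit 2). Adding the plan's own 56-day interval gives Day 57 as the earliest repeat donation.
- Visit 8 (1 month after the second transfusion) is Day 65-72: 65 - 57 = 8 and 72 - 57 = 15 days later.
- Visit 9 (2 months) is Day 95-102: 38 to 45 days later.

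Both draws that determine 1-month and 2-month recovery of the stored cells can follow a repeat donation.

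**The plan's own power figure.** Section 2.5.1 gives 15 versus 20 subjects, a 13-point difference, SD 12.5 and 84% power at 30 days. Taking alpha 0.05 as two-sided (sidedness is not stated), the t-test noncentrality is 13 / (12.5 × √(1/15 + 1/20)) = 13 / (12.5 × 0.3416) = 3.04 on 33 degrees of freedom. Power is 84.0%, so the figure reproduces and the same test is used below.

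**Effect of one donation.** Inputs: 500 mL per donation (Visit 2); 60-day recovery 50% with SD 10, and SD 12.5 in the power statement (Section 2.5.1); blood volume 4 to 6 L (assumption). The share of labelled cells removed is f = 500 / blood volume, and the apparent recovery is 50 × (1 - f).

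| Blood volume | f | Apparent 60-day recovery | Shift (points) |
|---|---|---|---|
| 4 L | 12.5% | 43.8% | 6.3 |
| 5 L | 10.0% | 45.0% | 5.0 |
| 6 L | 8.3% | 45.8% | 4.2 |

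If survival is read as a count, the fall is immediate. If it is read as a labelled fraction, the donation removes labelled and unlabelled cells alike; the fraction falls only as new unlabelled cells replace the loss, and the table is an upper bound.

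**Group bias.** Bias = shift per donor × difference between groups in the share who donate. The false-positive rate is the chance of p < 0.05 with no true difference, 15 versus 20, using the 60-day values alone.

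| Share donating (one group vs other) | Bias at 5 L | False-positive rate at 5 L (SD 12.5 to 10) | Same, over 4-6 L |
|---|---|---|---|
| 10% vs 0% | 0.5 | 5.1-5.2% | 5.1-5.4% |
| 25% vs 0% | 1.25 | 5.9-6.5% | 5.6-7.3% |
| 50% vs 0% | 2.5 | 8.8-11.0% | 7.6-14.4% |

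**The study's own draws, for scale.** Visits 6 to 9 take 14 + 8 + 12 + 12 = 46 mL, or 46 / 5000 = 0.9% of 5 L; with the optional 20 mL it is 66 / 5000 = 1.3%. The scheduled draws are the same in every group. A 30 mL loss is 30 / 5000 = 0.6%, or 0.3 points at 50% recovery.

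**The case against.** Several stronger readings are tempting, and the documents do not support them.

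- **That nothing would record bleeding.** Adverse events are assessed at Visits 3 to 10, a CBC is taken at Visits 6 to 10, and history is reviewed at Visit 6. A clinically important bleed could well be seen. This does not cover a voluntary donation: it is not an adverse event, the adverse event form takes only clinically important events (Section 6.4.5), and a CBC gives neither the cause nor the volume of a loss.
- **That carriers are habitual donors, so the bias runs towards a false reduction in their recovery.** Section 2.2.1 does say "A subset of REDSIII RBC Omics donors with candidate SNPs will be recalled to provide a blood sample to be tested for functional effects". However, Section 2.5.1 brings only 20 such subjects into the infusion study. The sickle-trait group is defined by self-identified race and electrophoresis (Section 3.2), and donors from the same cohort may serve as biotin controls (Section 5.1). No donation rate is given for any group.
- **That the error rate could be very high.** At 5 L it reaches about 21% to 30% only if every carrier and no control donates.
- **That donation could explain the planned sickle-trait effect.** That difference is 25 points at 60 days; one donation moves one subject by about 5.

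The calculation is also simplified. The primary model uses three time points, and the 2-4 hour value cannot be affected. The 1-month value is affected only by a donation in the preceding 15 days at most. Twenty recalled carriers spread over several genes would give fewer than 15 per comparison, so the same bias would yield fewer false positives.

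Finally, an instruction not to donate may stand in the consent form, which is not part of the text available here. Even so, recording and analysis rules belong in the protocol. Possible onward transfusion of a donated unit is a separate matter and carries no weight here.

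**Conclusion.** The gap holds. After baseline, donation by infusion subjects is not addressed in the instructions, the visit schedule or the analysis, and the survival ratio would count the cells removed as lost.

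The effect is modest: up to about 4 to 6 points in a subject who donates once, and roughly 1 to 3 points between groups if a quarter to a half of one group and none of the other donate. This rests on an assumed blood volume of 4 to 6 L, one 500 mL donation after Day 57, and full replacement of the lost cells if a fraction is measured. A bias against carriers is plausible for the 20 recalled-donor SNP subjects but not established, and the design gives no reason to expect it in the sickle-trait group. It matters mainly for SNP effects smaller than the planned 25 points. It is worth correcting because the remedy is cheap and the missing information cannot be recovered afterwards.

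**What to change.** - **Sections 2.2.2 and 2.3.7:** ask infusion subjects not to donate blood, and not to give optional RBC-OMICs draws (about 48 mL each), from Visit 2 until their last survival draw.
- **Visits 4 to 10 and Appendix A:** record any donation, non-study phlebotomy or notable bleeding, with date and estimated volume.
- **Section 2.5.2:** pre-specify that survival values after a whole-blood or red-cell donation are corrected for the recorded volume or excluded, with the uncorrected analysis as a sensitivity check. State whether survival is a count or a labelled fraction, because this decides the correction. With full replacement, dividing by (1 - f) restores the value: 45 / (1 - 0.10) = 50. Soon after a donation, a fraction would be over-corrected. Say how excluded values enter the imputation in Section 2.5.3.
- **Small losses:** do not delete values for losses comparable to the study's own 46 mL. The 30 mL figure in Section 3.3 is attached to diagnostic phlebotomy at entry and is not a suitable deletion threshold.

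The cost is one instruction, one question per visit and a few sentences in Section 2.5.2. A regular donor forgoes one or two donations, and a few values may be corrected or excluded.
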